## **4.0 STUDY DESIGN**

This is a multi-center, non-blinded randomized controlled trial in fetuses with isolated moderate CDH, i.e. moderate lung hypoplasia (as determined by prenatal assessment of lung development). It essentially compares fetal therapy added to conventional postnatal care, versus expectant prenatal management during pregnancy followed by conventional postnatal care.

There are currently 11 participating centers, of which seven see moderate only cases, one sees severe only cases, and three see both severe and moderate cases. Dr. [name] in Tokyo, Japan is preparing to join the study. As sites are added to the study, they are updated in the main study's website, <http://www.totaltrial.eu> and at [www.ClinicalTrials.gov](http://www.ClinicalTrials.gov) (NCT00763737).

Lead Investigator	Institution(s)	Case Type	Country
[name]	University Hospitals Leuven	Severe and Moderate	Belgium
[name]	Baylor College of Medicine Texas Children's Hospital	Moderate	United States of America
[name]	Hospital Clínic, University of Barcelona	Moderate	Spain
[name]	Hôpital Antoine Bécclère	Severe and Moderate	France
[name]	Hôpital Necker – Enfants Malades	Severe and Moderate	France
[name]	King's College Hospital	Moderate	United Kingdom
[name]	University Hospital of Bonn	Moderate	Germany
[name]	Mater Mother's Hospital	Moderate	Australia
[name]	Ospedale Maggiore Policlinico	Moderate	Italy
[name]	Ospedale Pediatrico Bambino Gesù	Moderate	Italy
[name]	Mount Sinai Hospital	Severe	Canada

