## 5.2 Inclusion Criteria

FETUSES:

1. Left-sided diaphragmatic hernia
2. Fetuses presenting at the latest at 31 weeks plus 5 days (intervention at the latest on 31 weeks plus 6 days).
3. Severity: Predicted moderate pulmonary hypoplasia. The degree of hypoplasia will be determined by the ultrasonographic measurement of the observed to expected lung area to head circumference ratio (O/E LHR) in a FETO center at entry to the study, at the latest the day before occlusion, but ideally between 26 and 31 weeks for practical reasons. (The O/E LHR is a measure that is gestational age independent.)

The following criteria for moderate pulmonary hypoplasia will be used: • O/E LHR 25-34.9% (included) irrespective of the liver position, or • O/E LHR 35-44.9% (included) with intrathoracic herniation of the liver.

In this group there is a predicted risk for postnatal death of 40% or higher and the risk of broncho-pulmonary dysplasia in case of survival is 33% or higher.

4. Chromosomally normal fetus.

5. Fetus with no major anomalies that would impact the clinical course or outcomes.

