### **6.7.1 Postnatal Death**

Permission should be requested for full postmortem examination in all cases of fetal or postnatal death. If this is not granted then permission for an MRI or CT examination and histological

examination of open lung biopsies should be requested. If none of the above is possible the cause of death will be determined on the basis of clinical findings.

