#### Primary Analysis:

The primary analysis will compare the proportion of subjects who are surviving till discharge and the survivors requiring no oxygen at 6 months of age. The primary analysis will be based on the intent-to-treat principle.

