- Preterm pre-labor rupture of the membranes and as a consequence preterm labor prior to in utero reversal of the occlusion, with as a consequence "incomplete" prenatal therapy as well as problems directly due to the inability or difficulties to remove the balloon, may result in lower than expected survival chances. When this happens, it will cause delivery at one of the FETO centers, therefore leading to a higher than expected number of babies delivered at these institutions. However this is inherent to the prenatal therapy and not avoidable. A separate secondary analysis may be done as to judge on the biological effect of the complete course of prenatal therapy (balloon insertion and balloon removal followed by birth in the un-occluded state), but again, results will be reported on an intention to treat - basis.
- In the fetal treatment arm there is the potential of patients not complying during the period the airways are plugged, presenting in an emergency at their local center, or for whatever reason not returning to the FETO center for balloon removal. This may adversely affect the outcome in the treatment group, lead to a higher than expected death rate in that arm. It could only be

discounted by post hoc exclusion. This will however not be done, as it is considered as an inherent risk of prenatal therapy. Such an effect may however be documented in a secondary analysis as described above.

- Prenatal medical imaging techniques may fail to recognize a concomitant congenital anomaly that is therefore only diagnosed after birth. Since serious associated anomalies are an independent predictor of outcome, and their numbers should be low, patients may not be equally distributed in both treatment arms. These patients will be excluded post hoc from analysis. It will include patients with serious genetic anomalies (not known at the time of FETO), undiagnosed structural cardiac or other structural anomalies that directly compromise neonatal outcome. Analysis of cases to be excluded will be overseen by the Data Monitoring and Safety Committee (also referred to as Oversight Committee).

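### The primary survival analysis is declared intent-to-treat, yet randomised babies with an anomaly found after birth are removed from it, with no closed list of diagnoses and no stated masking

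*Combined protocol and SAP*

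**What the plan says.** Under the Primary Analysis heading, section 9.2 states: "The primary analysis will be based on the intent-to-treat principle". The sources-of-error list in the same section restates that basis when it discusses incomplete prenatal therapy. For mothers who do not comply while the airway is occluded, it says the effect could only be "discounted by post hoc exclusion. This will however not be done, as it is considered as an inherent risk of prenatal therapy".

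The next bullet takes the opposite course for anomalies that prenatal imaging missed: "These patients will be excluded post hoc from analysis". Two groups are named. One is serious genetic anomalies that were unknown when FETO was done. The other is "undiagnosed structural cardiac or other structural anomalies that directly compromise neonatal outcome". The reasons given are that such anomalies predict outcome independently, should be few, and may fall unequally between the arms. The data monitoring and safety committee oversees which cases are excluded.

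Three other places bear on this:

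- Section 4.0: "This is a multi-center, non-blinded randomized controlled trial in fetuses with isolated moderate CDH".
- Section 5.2, fetal criterion 5, requires: "Fetus with no major anomalies that would impact the clinical course or outcomes".
- Section 6.7.1: "Permission should be requested for full postmortem examination in all cases of fetal or postnatal death".

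**The concern.** The text supports two different primary populations: all randomised, or all randomised less those excluded for a late-diagnosed anomaly. Two statisticians could each follow it faithfully and report different primary results. The secondary analyses in section 9.2 do not restore the excluded babies.

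The anomaly predates randomisation, but the decision to exclude comes after birth, when arm is known and survival may be. Several features let that decision depend on arm and outcome:

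- The structural criterion can mean a type of anomaly, as in entry criterion 5, or the effect the anomaly had on that particular baby. On the second reading, exclusion depends on the endpoint itself. Categories are named, but there is no closed list of diagnoses and no time limit for diagnosis.
- The reference time for genetic anomalies is the FETO procedure, which the expectant arm does not have.
- Postmortem is requested after deaths, so deaths may be searched more deeply than survivors. This applies in both arms, so on its own it does not bias the test. It does supply mostly deaths as candidates for a decision that is not stated to be masked.
- The committee is not stated to be masked to arm or survival.

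What is at stake is the confirmatory survival test, including each interim look that can stop the trial.

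**Working it through.** **Inputs.** From section 9.1: one-sided alpha 2.5%; power 80%; survival 40% v 60%; 40, 59, 69, 79, 89 and 98 per arm at the six looks; p-boundaries 0.0005, 0.0036, 0.0064, 0.0099, 0.0140 and 0.0186. From section 9.2: z-test for two proportions. The documents give no exclusion rate, so every removal share below is an assumption.

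**The plan's own figures.** An O'Brien-Fleming boundary has z = C/√t at information fraction t. With t = 0.4, 0.6, 0.7, 0.8, 0.9 and 1, numerical integration gives C = 2.0834. The final p is 1 − Φ(2.0834) = 0.0186, and the other five p-values match the table. The sample size comes to 97.8, rounded to 98 per arm. The final difference is 2.0834 × √[(0.4×0.6 + 0.6×0.4)/97.8] = 0.146, as printed. The design is reproduced.

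**How few babies matter.** The test is z = (p_F − p_C)/√[p(1−p)(1/n_F + 1/n_C)], where p is the pooled proportion. At the final look (boundary 0.0186):

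| Survivors, control v FETO | Difference | z | One-sided p | Crosses? |
|---|---|---|---|---|
| 42/98 v 56/98 | 0.143 | 2.00 | 0.0228 | no |
| 42/98 v 56/96 (two FETO deaths dropped) | 0.155 | 2.16 | 0.0156 | yes |
| 42/96 v 56/96 (two deaths dropped per arm) | 0.146 | 2.02 | 0.0216 | no |
| 39/98 v 54/98 | 0.153 | 2.15 | 0.0160 | yes |
| 39/96 v 54/98 (two control deaths dropped) | 0.145 | 2.02 | 0.0218 | no |

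These counts were chosen near the boundary to show sensitivity. They are not forecasts.

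**Operating characteristics.** The six-look design was simulated with 2,000,000 trials per scenario. Each death (and, where stated, each survivor) was removed independently with the given probability and not replaced. True survival was 50% in both arms for type I error.

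| Removal (assumed) | Type I error |
|---|---|
| None | 2.6% |
| 5% of FETO deaths only (98×0.5×0.05 ≈ 2.5 babies) | 3.7% |
| 10% of FETO deaths only (≈ 4.9 babies) | 5.4% |
| 5% of control deaths only | 1.6% |
| 10% of control deaths only | 1.0% |
| 10% of FETO deaths and 5% of FETO survivors, no controls | 3.8% |
| Modest imbalance, FETO v control: 6% v 4% of deaths, 3% v 2% of survivors | 2.8% |
| Mirror image of the modest imbalance | 2.3% |
| Equal removal of deaths in both arms, or one arm at the same rate in deaths and survivors | 2.5–2.6% |

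**Power and estimate at 40% v 60%.** With no exclusions, power is 79%. Removing a fraction r of control deaths only makes the apparent difference 0.60 − 0.40/(1 − 0.60r). At r = 0.05 this is 18.8 points with power 73%. At r = 0.10 it is 17.4 points with power 66%.

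**The case against.** The best defence is that the exclusion is written in advance, gives its reasons, and removes babies who would have failed entry criteria 4 or 5 had the anomaly been known. The target condition is isolated CDH, and the feature predates randomisation. Exclusion on fixed criteria, masked to arm and outcome, would leave the test valid. On this view the anomaly bullet is a specific exception to a general principle, and what is missing is only detail on how it is applied.

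Much of that is fair. The harm needs exclusion to differ by both arm and outcome. Removal from one arm only is an extreme, and the modest imbalance moves type I error by only about 0.2 to 0.3 points. Postmortem is requested in both arms. Section 9.2 also describes the committee as not otherwise involved in the study.

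It does not settle the matter. Independence is not masking, and section 9.2 supplies none of the conditions that would make the exclusion safe. The stated worry about unequal distribution describes chance imbalance, which randomisation and the test already allow for. The intent-to-treat commitments might be read as keeping an all-randomised analysis, but the plan does not say so where it excludes these babies. Small expected numbers are little comfort when two babies can reverse a result near the boundary.

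**Conclusion.** The concern holds and should be fixed before the primary analysis. The conflict over who is counted in the primary survival test is in the text and rests on no assumption. The size of the bias does rest on assumptions, because the documents say only that such cases should be few. The illustrated type I error runs from 1.0% to 5.4% with one-arm removal of up to 10% of deaths, is 2.3% to 2.8% under modest imbalance, and stays at about nominal when removal is equal in both arms or unrelated to outcome. The direction cannot be known in advance. Without an all-randomised result, a reader could not tell which case applied. The figure of 98 per arm and the boundaries are not in question.

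**What to change.** In the sources-of-error list of section 9.2, state that every randomised fetus stays in the primary and co-primary analyses, at each interim look and at the end. Report the anomaly exclusion only as a labelled sensitivity analysis, with:

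- a fixed list of qualifying anomalies, defined by type and not by the effect on the individual baby;
- adjudication masked to arm and survival;
- one reference time for both arms: present but unknown at randomisation;
- the number excluded, by arm and by survival status.

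Align the missing-data rule in the same section, which drops cases without a survival result from the study, so that the two rules do not conflict.

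The work is revised wording, one short list and one table; sample size and boundaries do not change. Section 10.1 requires prior IRB and FDA approval for an amendment. Section 9.2 indicates that two interim analyses have already taken place, so the amendment should record who had seen results by arm when the change was made.

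The statistical cost is that a few non-isolated cases dilute the effect. Suppose a share e of each arm has such an anomaly, all of them die, and 40% v 60% applies to the rest. Survival is then 0.40(1−e) v 0.60(1−e). Power with everyone kept is 77.6%, 76.8% and 74.9% for e = 2%, 3% and 5%, against 78.5%, 78.1% and 77.0% with equal exclusion in both arms. That is a loss of about 1 to 2 points.

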## **Outcome measures**

Primary outcome measures:

- Survival until discharge
- Supplemental oxygen at 6 months of age.

Secondary postnatal outcome measures:

- Grade of oxygen dependency (grade 0-III; definition as above)
- Occurrence of severe pulmonary hypertension (yes / no; based on evidence on cardiac ultrasound)

of predominant unidirectional right to left shunt) in the neonatal period 

- Need for ECMO support for centers offering it (yes / no) 
- Defect size as per classification by the CDH study group
- Number of days in neonatal intensive care unit (days); (if death occurs; day of death)
- Number of days of ventilatory support (days) ;
- Presence of periventricular leucomalacia at  $\leq 2$  months postnatally (yes / no)
- Presence of neonatal sepsis (yes/no)
- Presence of intraventricular hemorrhage (grade 0-III)
- Presence of retinopathy of prematurity (grade III or higher)
- Number of days till full enteral feeding (days)
- Presence of gastro-esophageal reflux (above one third of the esophagus on clinically indicated radiologic study)
- Day of surgery (days)
- Use of a patch (yes/no)

Secondary prenatal outcome measure:

- Lung volume as serially measured by 2D-ultrasound and/or fetal MRI (o/e LHR, o/e total lung volume)
- Liver position; in case of liver herniation, the liver-to-thorax volume.

Secondary longer term outcome variables:

- Pulmonary function and volume testing before and after repair, at discharge, and at one year of age
- Neurodevelopmental milestones at discharge, 12 months and 2 years (AGES and STAGES, validated English and Spanish questionnaires). Use of this questionnaire does not depend on additional funding.
- Death at 2 years (due to either primary illness or other causes)

### **9.3 SAFETY EVENTS/Reporting**

The Investigator is responsible for the detection, documentation and follow-up of all safety events

meeting the criteria and definitions outlined below in subjects enrolled on this protocol. For purposes of this protocol subjects can be mother, fetus, and/or infant/child up to 2 years of age.

### **9.3.2 Definition of Safety Event**

A safety event is any untoward medical occurrence, unintended disease or injury or any untoward clinical sign (including a clinically significant abnormal laboratory finding) in subjects whether or not related to the investigational devices or to the procedures involved (including any procedure in the clinical study protocol).

### **9.4 Not Device or Procedure Related – Adverse Event (AE)**

Safety events which are not related to the investigational device or the procedure to place the balloon are referred to as Adverse Events (AEs).

### **9.5 Device or Procedure Related – Adverse Device Effect (ADE)**

An Adverse Device Effect (ADE) is a safety event related to the use of an investigational medical device. This includes any safety event resulting from insufficiencies or inadequacies in the Instructions for use, the deployment, placement, operation, or any malfunction of the investigational medical device(s). This includes any event that is a result of a use error or intentional misuse.

### **9.6 Definitions of Serious Safety Events**

A safety event is serious if the event:

- Led to a death.
- Led to a serious deterioration in health that either:
- Resulted in a life-threatening illness or injury, or
- Resulted in an injury or permanent impairment of a body structure or a body function, or
- Required in-subject hospitalization or prolongation of existing hospitalization, or
- Resulted in medical or surgical intervention to prevent life threatening illness.
- Led to fetal distress, fetal death or a congenital abnormality or birth defect.

This includes deficiencies that might have led to a serious adverse event if:

- Suitable action had not been taken or
- Intervention had not been made or

A planned hospitalization for a pre-existing condition, or a procedure required or described as a possibility by the protocol as part of procedures performed in regular clinical care, without a serious deterioration in health, is not considered to be a serious safety event. Events that occur after birth that are related to the underlying condition (CDH) and which are unrelated to this protocol (such as a complication with ECMO or other forms of neonatal treatment for CDH) will not be considered to be a serious safety event of the balloon placement.

### **9.7 Not Device or Procedure Related – Serious Adverse Event (SAE)**

A Serious Adverse Event (SAE) is a safety event that has resulted from a serious safety event as assessed by the investigator and is not device or procedure related.

### **9.8 Device or Procedure Related – Serious Adverse Device Effect (SADE)**

A Serious Adverse Device Effect (SADE) is a device or procedure related safety event that has resulted from a serious safety event and is an event by its nature, incidence, severity or outcome that has been previously identified in the Risks section (Section 7.0) of this protocol.

### **9.9 Unanticipated – Unanticipated Adverse Device Effect (UADE)**

An Unanticipated Adverse Device Effect (UADE) is defined as any serious adverse effect on health or safety or any life-threatening problem or death caused by, or associated with, the Investigational device(s), if that effect, problem, or death was not previously identified in nature, severity, or degree of incidence in the clinical study protocol, Report of Prior Investigations, or application (including a supplementary plan or application), or any other unanticipated serious problem associated with an investigational product that relates to the rights, safety, or welfare of subjects (21 CFR 812.3(s)).

### **9.10 Safety Event Assessments**

All safety events will be monitored in conjunction with the study assessment schedule and will be reported to the IRB and FDA on an annual basis in the IDE Progress Report.

Unanticipated events will be collected, assessed and reported according to SOP P-15-XX-Documentation and Reporting of Serious Adverse Events and Unanticipated Problems.

The Sponsor (IDE holder) will be responsible for reporting all reportable unanticipated events to the appropriate regulatory agencies (e.g., IRB, FDA) as per each agency's individual reporting requirements and within that agency's required time frame.

### **9.11 Assessment of Causality**

The Investigator will assess the relationship between each safety event and both the device and the procedure using the definitions listed below. Note that a safety event may be related to the device or the procedure or both. The Investigator should assess causality of each safety event to the device independent from the procedure and to the procedure independent from the device.

### **9.12 Investigational Product**

- **Definitely Related:** The safety event has a strong temporal relationship to the device. The safety event is most likely explained by device. The safety event is consistent with a known response to the device. Another etiology is unlikely or significantly less likely.
- **Probably Related:** The safety event has a strong temporal relationship to the device. The safety event is more likely explained by the device than by another cause.
- **Possibly Related:** The safety event has a reasonable temporal relationship to the device.

The safety event could have been due to another equally likely cause.

- Not Related: The subject did not receive the device OR the safety event has no temporal relationship to the device OR the safety event has a much more likely alternate etiology OR the safety event is due to an underlying or concurrent illness or effect of another drug.

### **9.13 Procedure**

- Definitely Related: The safety event has a strong temporal relationship to the procedure. The safety event is most likely explained by the procedure.
- The safety event is consistent with a known response to the procedure. Another etiology is unlikely or significantly less likely.
- Probably Related: The safety event has a strong temporal relationship to the procedure. The safety event is more likely explained by the procedure than by another cause.
- Possibly Related: The safety event has a reasonable temporal relationship to the procedure. The safety event could have been due to another equally likely cause.
- Not Related: The subject did not have the procedure OR the safety event has no temporal relationship to the procedure OR the safety event has a much more likely alternate etiology OR the safety event is due to an underlying or concurrent illness or effect of another drug.

Even in situations in which minimal information is available for the initial safety event, it is important that the Investigator always make an assessment of causality for every event. The causality assessment is one of the criteria used when determining regulatory reporting requirements. The Investigator may change his or her opinion of causality in light of follow-up information and amend the report accordingly.

All safety events must be followed until they are resolved, the condition stabilizes, the events are otherwise explained, or the subject is lost to follow-up.

### **9.14 Serious Safety Events, Reporting Requirements**

Once the Investigator determines that a safety event meets the definition of serious (SAE or SADE), the Sponsor-Investigator will provide an assessment within 5 days of becoming aware of the event.

